2.2 Secondary Objectives

- 1) To collect data on biomarkers of treatment efficacy, toxicity, and liver function to plan further enhancements to individualized RT.
- 2) To determine the change in quality of life during and after RT.

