5.5 Duration of Follow-Up

Patients will be followed for 2 years after completion of treatment or until death, whichever occurs first. If patients progress outside of the treated tumor, they will only be followed for survival, without mandated visits with study personnel, as long as they are being seen routinely every 3-6 months by an oncologist or hepatologist. These clinic notes can be requested for study purposes, and tumor measurements tracked from clinical scans.

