5.6 Off Study Criteria

Patients can be taken off study at any time at their own request, or they may be withdrawn at the discretion of the investigator for safety, behavioral or administrative reasons. Patients will be considered off study after completion of protocol treatment and follow-up criteria.

The reason(s) for discontinuation from study will be documented and may include:

5.6.1 For patients planning to receive ICG testing in lieu of ALBI, patients will be removed if

- they are unable to complete the pre-treatment and post- 3 fraction IC Green tests, as these are necessary for dose adjustment.
- 5.6.2 Patients will be removed if they are unable to receive RT treatments.
- 5.6.3 Patients may be removed from study at any time by patient request.
- 5.6.4 Patients who enroll in subsequent liver radiation therapeutic trials are considered off study for initial enrollment. Local control for all treated lesions will be tracked on the follow up schedule for the subsequent enrollment to avoid duplicate procedures.
- 5.6.5 Patients who have progression of the treated lesion will be followed for survival and toxicity only.
- 5.6.6 Patients who go on to receive additional liver-directed to the treated lesion or systemic therapy (non-radiation therapy, on or off protocol) will be followed for survival only.
- 5.6.7 Patients can be removed from study if they are unable to comply with protocol requirements.
- 5.6.8 Patients can be removed from study if the treating physician judges that continuation on the study would not be in their best interest.

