6.3 Follow-Up Procedures

Patients will be evaluated approximately 1 month after completion of therapy and then at approximately 3-6 month intervals until 2 years. Evaluation will include H&P, laboratories (CBC, comprehensive metabolic panel, INR, AFP if elevated at diagnosis), and liver imaging (beginning 3 months after treatment). QOL assessments will be obtained at the same intervals for 1 year. ICG or ALBI will be assessed approximately 1 and 3 months after completion of therapy. Blood and urine (when patient is able to provide) will be collected at approximately 1 and 3 months after completion of therapy. MRI will be assessed approximately 1 month after completion of therapy. This follow up schedule will adhere to standard of care clinical follow up. Therefore, missed visits and visits that diverge from this regimen will not be considered protocol deviations. MRI and ICG must be performed at the University of Michigan. However, if patients are not able to travel for all other follow up evaluations and procedures, they may have these performed by a local physician and records obtained by the study team. If patients are concurrently or previously enrolled in another research study which requires similar testing, all efforts will be made to avoid unnecessary repeat testing.

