6.4 Time and Events Table

	Pre-Rx Eval ¹	Initial RT Phase	Active Treatment	
			Evaluation Period Approximately 4-6 Weeks after Initial RT Phase	Final RT phase ⁵
History, Physical Exam, Performance Status, QOL⁸	X	PS	QOL	PS
Weight	X	Once	X	Once
CBC/Platelets	X		X	
AST, ALT, Alk Phos, Bilirubin	X		X	
BUN/Creatinine	X		X	
INR	X		X	
AFP (for HCC)	X		X	
Toxicity Notation	X	Once		Once
MELD/CTP assessment	X		X	
IC-Green⁶	X		X ⁴	
Simulation	X		X	
Perfusion MRI⁹	X		X	
Tumor biopsy⁷	X			
Diagnostic CT or MRI of liver	X ²			
Chest imaging with x-ray or CT	X ³			
Plasma and serum	X		X	
Radiation Treatment (RT)		X		X

¹ From 30 days prior to signed ICF, through treatment start.

² From 90 days prior to signed ICF, through treatment start.

³ Within 1 year prior to enrollment

⁴ If a patient does not initially qualify for the final RT phase, he/she will undergo repeat IC-Green in approximately 4 weeks as a second attempt.

⁵ Patients who do not qualify for the final RT phase will not undergo any of the treatment or testing associated with that phase. The final day of the initial RT phase will be counted as the last day of treatment, and the follow up calendar will be initiated.

⁶ For patients indicated to receive IC-Green from the treating physician. If the patient was previously enrolled on any trial utilizing IC-Green (including this one), then an evaluation of IC-Green retention performed for the other trial may be used as the pre-treatment assessment for this enrollment, as long as it is within 30 days prior to initiation of this new course of RT.

⁷ Biopsy only performed if patient consents

⁸ QOL will consist of the Functional Assessment of Cancer Therapy-Hepatobiliary (FACT-HEP) version 4. As patients can be seen in a variety of clinics, and occasionally do not follow a standard clinic schedule, missed QOLs will not be reported as a protocol deviation.

⁹ Description of Perfusion MRI protocol in the appendix.

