Quality of life will be summarized descriptively at baseline (pre-RT) and at each post RT timepoint. Change from baseline will be calculated for each patient and summarized descriptively as well as tested for statistical significance using a paired t-test.

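### The paired t-test for quality-of-life change uses only patients with both forms; follow-up rules make this a selected, probably healthier group, and a repeated-measures model would serve better

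*Combined protocol and SAP*

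**What the plan says.** Section 2.2 lists as its second secondary objective "To determine the change in quality of life during and after RT". The whole analysis is in section 11.3: "Quality of life will be summarized descriptively at baseline (pre-RT) and at each post RT timepoint", after which each patient's change from baseline is described and "tested for statistical significance using a paired t-test". No rule for missing forms, longitudinal model, sensitivity analysis or report of completion is given.

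Forms are taken at baseline and at the mid-treatment evaluation (section 6.4). After treatment, section 6.3 sets visits at about 1 month and then every 3 to 6 months, and says "QOL assessments will be obtained at the same intervals for 1 year".

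Loss of forms is foreseen in four places:
- Section 6.3: "missed visits and visits that diverge from this regimen will not be considered protocol deviations".
- Section 6.4, footnote 8: "missed QOLs will not be reported as a protocol deviation".
- Section 5.5: "If patients progress outside of the treated tumor, they will only be followed for survival, without mandated visits with study personnel".
- Section 5.6.5: "Patients who have progression of the treated lesion will be followed for survival and toxicity only". Section 5.6.6 limits follow-up to survival after further liver-directed treatment of the lesion or systemic therapy.

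**The concern.** A paired t-test needs two forms from the same patient. A patient who returns the early forms and then stops contributes nothing to the later comparisons, although the early forms may already show decline. In this trial the reasons for stopping include progression and further therapy, and death removes others. Section 3.1 admits Child-Pugh B8 and above and asks for a life expectancy of only 12 weeks, while QOL runs for a year. Section 11.2 plans on a toxicity rate of about 20%.

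If patients who are doing worse leave sooner, each later visit describes a healthier group than the one treated, and a different group each time. At stake is the answer to a secondary objective, and a possibly optimistic QOL profile carried into the planning of the randomized trial.

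**Working it through.** **Is there a figure to reproduce?** No. The only usable input is 80 evaluable patients (section 11.2). The documents give no QOL effect, SD, correlation, significance level or expected missing rate. Everything numerical below is assumed and illustrative.

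**Direction of the bias.** Let D be a patient's change and R = 1 if the later form is returned. The paired mean estimates

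E(D | R = 1) = E(D) + Cov(D, R) / P(R = 1).

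If R is unrelated to D, the covariance is zero, the mean is unbiased and only sample size is lost. If worse patients return fewer forms, the covariance is positive and the decline is understated.

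**Illustration 1: dropout depends on QOL change already observed.** Assumed: 80 patients; forms at 0, 1, 4, 8 and 12 months; score SD 1; correlation 0.5 + 0.5 × 0.9^lag (lag in months); true 12-month change -0.30; about 57% retained at 12 months; log-odds of dropout rising by a fixed slope per 1 SD of earlier decline; two-sided 5% test.

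Power check with no dependence:
- Correlation between 0 and 12 months = 0.5 + 0.5 × 0.9^12 = 0.641.
- SD of change = √(2 × (1 - 0.641)) = 0.847.
- Standardized change = 0.30 / 0.847 = 0.354.
- Retained n = 0.57 × 80 ≈ 46, so the noncentrality is 0.354 × √46 = 2.40 and power is about 65%.

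That 65% is the fair comparator: it is the cost of losing patients before any bias.

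| Slope (odds ratio) | Paired mean | Power of t-test | Likelihood model |
|---|---|---|---|
| 0 (1) | -0.30 | about 65% | about -0.30 |
| 0.5 (e^0.5 = 1.6) | -0.23 | about 45% | about -0.30 |
| 1 (e^1 = 2.7) | -0.16 | about 25% | about -0.30 |
| 2 (e^2 = 7.4) | -0.06 | about 8% | about -0.30 |

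The model's SD is equal or nearly equal to that of the paired mean. The paired means move by a few hundredths of an SD with details such as when dropout can begin. The ordering does not change.

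**Illustration 2: dropout depends on the change at that same visit.** Here the unit is the SD of the change, so power is not comparable with the table above. With all 80 forms the noncentrality is 0.30 × √80 = 2.68 and power is 75.5%. With forms lost at random the mean stays at -0.30, and power is 66% at n = 64 and 60% at n = 56. With the odds of a missing form multiplied per 1 SD of worse change, the responder mean (power) is:

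| Missing | Odds ratio 1.5 | Odds ratio 2 | Odds ratio 3 |
|---|---|---|---|
| 20% | -0.22 (42%) | -0.17 (29%) | -0.11 (16%) |
| 30% | -0.18 (28%) | -0.11 (14%) | -0.03 (6%) |

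**What the model does when forms are not missing at random.** In the setting of illustration 1, but with dropout driven by the unseen score, the model gave -0.24 against -0.17 for the paired mean, and -0.17 against -0.06 at a stronger dependence. A separate simulation used four visits, correlation 0.6 and about 52 (odds ratio 2) or 49 (odds ratio 3) of 80 patients remaining. It gave -0.22 against -0.11 at odds ratio 2, and -0.16 against -0.01 at odds ratio 3. The truth is -0.30 throughout. The model is closer each time but does not recover the full change.

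**The case against.** **Footnote 8 gives logistics as its reason.** It says that patients attend various clinics and do not always keep a standard schedule. A reader might infer from it that worsening patients stop responding, but it does not say so. Taken alone it fits loss unrelated to QOL, which costs precision and causes no bias. The support for informative loss is in sections 5.5 and 5.6. Even these do not name QOL: that collection ends at progression is the natural reading, not a stated rule.

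**The size is a matter of choice.** This stands. No figure for the understatement can be taken from the documents, and weak dependence gives a small bias. A quoted drop in power also mixes bias with lost sample size unless it is set against 65%.

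**The model was tested on its own terms.** Its -0.30 comes from dropout simulated to satisfy missing-at-random. This stands, and is why the not-at-random results are shown and a sensitivity analysis belongs in the fix.

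**Death is not ordinary missing data.** Change among patients alive and assessed is a legitimate descriptive target. This stands: understatement is meaningful only against a stated target, so both quantities should be shown.

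**Early forms are not thrown away.** They enter the summaries at their own visits and go unused only for later visits.

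**Repeated testing.** A reader might infer a large excess of false positives across visits. Section 11.3 does not state that the test is repeated at each visit, the 3-to-6-month spacing leaves the number of visits open, and such tests would be correlated. No error rate can be attached, and intervals at each visit from a model would raise the same question.

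**Conclusion.** The point holds in a limited form. The paired t-test estimates change only in patients with both forms, and the follow-up rules make it likely that this group is selected and probably healthier. That conclusion rests on reading sections 5.5 and 5.6 as ending QOL collection, and on progression or further therapy being related to QOL. If neither matters, the only loss is precision.

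Under the assumptions above, a true change of -0.30 SD would appear as anything from -0.30 (no dependence) through -0.23 (weak) to between -0.16 and -0.06 (strong). The documents do not show which applies, so they do not support a claim that the trial will understate decline by a given amount.

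The consequence is modest. QOL is a secondary objective of a single-arm pilot, is not among the endpoints in section 2.3, and plays no part in the section 11.2 criterion for phase II, which uses toxicity and local control. The change is desirable and cheap, and nothing in the trial's main decision depends on it.

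**What to change.** In section 11.3, replace the paired t-tests with one mixed model for repeated measures on all available FACT-Hep forms, including the mid-treatment form, with visit as a factor and an unstructured covariance. Define visit windows first, because the 3-to-6-month spacing varies between patients. Report change from baseline at each visit with a 95% confidence interval, and name one FACT-Hep score and one main time point.

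Alongside it:
- Tabulate forms received, deaths and reasons for missing forms by visit.
- State that the model estimate treats QOL after death as missing, and show the observed change among patients alive and assessed beside it.
- Add one delta-adjusted sensitivity analysis for data not missing at random.
- State whether QOL forms are still sought after progression or further therapy.

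The cost is SAP wording and slightly more analysis work, with no extra patients or procedures for the analysis changes. The downside is reliance on missing-at-random given the observed QOL, which is a weaker assumption than the paired t-test needs to describe all treated patients.

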12.0 DATA AND SAFETY MONITORING

This trial will be monitored in accordance with the NCI approved University of Michigan Comprehensive Cancer Center Data and Safety Monitoring Plan. The study specific Data and Safety Monitoring Committee (DSMC), consisting of the protocol investigators, data manager or designee and other members of the study team involved with the conduct of the trial, will meet quarterly or more frequently depending on the activity of the protocol. The discussion will include matters related to the safety of study participants (SAE/UaP reporting), validity and integrity of the data, enrollment rate relative to expectations, characteristics of participants, retention of participants, adherence to the protocol (potential or real protocol deviations) and data completeness.

At the regular DSMC meetings, the protocol specific Data and Safety Monitoring Report form will be completed. The report will be signed by the Principal Investigator or by one of the co-investigators.

Data and Safety Monitoring Reports will be submitted to the University of Michigan Comprehensive Cancer Center Data and Safety Monitoring Board (DSMB) on a quarterly basis

for independent review.

13.0 QUALITY ASSURANCE AND AUDITS

The Data Safety Monitoring Board can request a 'for cause' audit of the trial if the board identifies a need for a more rigorous evaluation of study-related issues. A "for cause" audit would be conducted by the Quality Assurance Review Committee (QARC) of the University of Michigan Comprehensive Cancer Center.

A regulatory authority (e.g. FDA) may also wish to conduct an inspection of the study, during its conduct or even after its completion. If an inspection has been requested by a regulatory authority, the site investigator must immediately inform the Clinical Trials Office that such a request has been made.

15. APPENDIX I

Liver MR Imaging Protocol (subject to minor change)

1. Breath-holding VIBE Dixon scan to obtain fat and water in-phase and out-phase, and calculated fat and water images, acquisition time ~ 20 seconds
2. Free-breathing internal-triggered T2 weighted scan, acquisition time 2-3 min
3. Free-breathing internal triggered diffusion weighted scan, acquisition time ~ 4 min
4. Free-breathing pre-contrast T1 weighted scan using a new starVIBE (or radialVIBE with radial sampling and suppressing motion artifacts) sequence, acquisition time ~ 1 min
Or breath-holding pre-contrast T1 weighted scan using a conventional VIBE sequence, acquisition time ~20 s
5. Free-breathing T1 weighted scan with contrast injection using the starVIBE (or RadialVIBE) sequence, to reconstruct low-spatial resolution dynamic contrast enhanced images, and high-spatial resolution arterial and portal vein phase images using either vendor provided online option or an offline in-house software . Acquisition time is ~3-4 min. **If gadoxetic-acid (Eovist) is chosen as the contrast agent, acquisition will be extended up to 20 min.**
6. A late phase T1-weighted scan using the same sequence
